**A6. Conceptual Framework for Evaluation**. We have adapted our conceptual framework from the WH PACT trial for the proposed evaluation (*Figure* below). In this evaluation, a contractor working under technical specifications for EBQI (*far left column*) will: 1) convene facility-level stakeholder meetings; 2) facilitate local facility-level QI team design meetings; and 3) provide external practice facilitation through within- and across-facility QI collaboration calls, QI data feedback and QI training/education. Initial results of EBQI implementation will include local QI actions (e.g., strategic project activities, structured QI proposals, and multilevel review in advance of conduct), and improved provider and staff QI orientation, WH

knowledge/awareness, and gender awareness (*middle column, top*). These actions will occur in the context of each VAMC's leadership support, local resources, pre-EBQI WH care model and staffing, pre-EBQI provider and staff QI and WH experience, awareness and attitudes, as well as area characteristics (e.g., urban/rural location) (*middle column, bottom*).

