# **B2. Evaluation Design**

The choice of a dynamic waitlisted design is based on WHS's plans for staged EBQI implementation at no more than eight VA facilities per year for the next three years for a total of 24 facilities. This randomized "roll-out" implementation design has very good statistical properties, including higher power than traditional

wait-listed designs and less vulnerability to external, uncontrolled factors. EBQI implementation will commence in Year 1 (FY17) in eight randomly selected facilities (Group 1), with the remaining 16 facilities serving as waitlisted controls. In FY18, eight of these waitlisted controls will be randomly selected for EBQI implementation (Group 2), leaving the remaining eight as waitlisted controls in FY18, which will begin EBQI implementation in Year 3 (Group 3).

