**B4c. VA Providers/Staff Surveys**. We will use web-based provider/staff surveys at baseline, 12- and 24months. Sampling Plan: We will obtain lists of local providers and staff using the same protocol used previously to identify PC and WH providers/staff, drawing a census from Primary Care Management Module (PCMM) data for each participating facility (including PACT teamlets and larger PACT teams [e.g., pharmacists, social workers]). In the 12-VA WH PACT trial, this approach yielded 775 providers and staff across urban and rural VAMCs; we anticipate identifying roughly twice as many personnel in the 24-facility evaluation. If other work units are prioritized by WHS (e.g., MH provider/staff), we will adapt the same approach but using VA PAID and other administrative sources, with local sample validation. Measures: We will include measures of *EBQI exposure/participation* (e.g., awareness, hours spent, local buy-in), *QI orientation/culture* (e.g., perceived cooperation among managers/providers/staff, communication effectiveness, culture fostering flexibility, participative decision-making), gender sensitivity (e.g., awareness, knowledge, attitudes, self-assessment of WH proficiency), practice context (e.g., leadership norms, organizational readiness to change, job satisfaction, burnout), and provider/staff *characteristics* (e.g., age, gender, race, ethnicity, staff type, clinician type, DWHP, proportion of WVs in panel/clinic, board certification, years in VA) (**Appendix 5**). Data Collection: Consistent with prior procedures, we will send pre-notification emails, then email invites with an embedded survey weblink, Q&A, and endorsement letters from WHS and local leadership. Email reminders will include a hardcopy option.

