B5b. Quantitative Analyses (Aim #2). To assess effectiveness of EBQI implementation on comprehensive care achievement, we will use data from the organizational surveys (§B4b), provider/staff surveys (§B4c) and administrative data on quality and patient experiences (§B4d). Dependent Variables: We will examine multiple outcome measures as dependent variables: 1) multiple individual measures of comprehensive care achievement, including levels of WH service availability (as noted in VHA Handbook 1330.01), integration of and access to gender-specific and MH care, and other related measures that capture different domains of comprehensiveness; 2) gender-sensitive care delivery, including organizational and provider/staff level measures; and 3) quality of care and patient experience measures. For comprehensive care achievement, we will include as dependent variables the individual measures, and we will also examine approaches to creating an aggregated ordinal score of the individual measures. We will prioritize the final set of dependent variables in consultation with WHS. Independent Variables: The primary regressors of interest will be EBQI exposure (i.e., level of implementation) and time. We will examine the potential moderating effects of practice context and provider/staff knowledge/attitudes (e.g., determine EBQI effects in high vs. low leadership support sites). We will use multiple linear or logistic regression to evaluate EBQI effectiveness. Where appropriate we will adjust for covariates, account for clustering of patients by site, and mitigate bias due to non-response or loss to follow-up through the use of enrollment/attrition weights. Covariates used for adjustment will include patient factors (e.g., facility casemix, proportion of WVs seen), provider/staff factors (e.g., DWHP availability, readiness), and organizational factors (e.g., resource sufficiency, facility size). Clustering by site will be accounted for by fitting hierarchical regression models with random intercepts for the sites (e.g., using SAS PROC Mixed). We will evaluate the goodness-of-fit of a given regression model using standard diagnostics (e.g., Mallow's statistic (Cn)). To adjust for potential non-response bias and loss to follow-up over time for the provider/staff survey samples, we will apply enrollment weights using available characteristics of eligible providers/staff and attrition or "inverse probability of inclusion" weights estimated using an appropriately specified logistic regression model. We will use multiple imputation methods to replace missing values among covariates with hot-deck methods used for imputation as needed. We will estimate site-level effects using the hierarchical regression models with random intercepts for sites. While our sample of sites (24) is small for the estimation site-level effects. EBQI trials of fewer sites have noted significant effects.

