
### **B6.** Potential Obstacles and Solutions

**B6a. Timing of Data Collection**. The evaluation's launch will be reliant on identification of low-performing VAs and WHS's introduction of EBQI plans with facility and VISN leadership. Once navigated, we will brief leaders of participating VAs regarding the evaluation, work with locally identified contacts, and begin sample development (KS, provider/staff). KS interviews will begin as soon as practicable, as will baseline administrative data extraction. Provider/staff surveys, however, will have to undergo review by the National Center for Organizational Development's Organizational Assessment Sub-Committee (OASC) as the evaluation meets the criteria of VA employees across 10+ sites. While no FY17 blackout dates have yet

been published, we will be required to accommodate them. As with prior work, we will also submit the surveys for national Union review, with a 30-day review period.

**B6b. Timing and Unit of Randomization**. The EBQI contractor was recently approved (8/22/16), enabling an early start on site selection. WHS has agreed to allow us to randomly allocate up to eight VA facilities of the 24 low-performers in Year 1, up to eight VAs of the remaining 16 in Year 2, with the remainder getting EBQI exposure in Year 3. If the EBQI contractor does not meet contract deliverables, evaluation activities may be delayed to accommodate their processes. Fortunately, the contractor (Atlas Research) has a strong track record with VA and specifically WHS. We plan to proceed with the evaluation even if not all contracted-for activities occur, enabling us to still address our evaluation aims. Low-performing facilities may also suffer from leadership gaps, provider and staff burnout, and other structural and management issues that may complicate their engagement in evaluation activities. We have experience working with VHA, VISN and VAMC leaders in multilevel research and evaluation, but will consider site replacement, depending on the circumstances.

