In Q2, we will continue with KS interviews, including WHS and EBQI contractor interviews and extending the KS sample to accommodate EBQI targets in Group 1 (e.g., MH leads). We will update the provider/staff survey sample lists, and work with site-level evaluation contacts on sample validation and updated cover letters as needed (i.e., to accommodate leadership changes). By the end of Q2, we will deliver KS summaries and organizational survey findings. We will launch the second wave provider/staff surveys in Q2. We will also pull a second year of administrative data, and provide WHS with a summary report on changes.

In Q3, we will finish the provider/staff survey wave, clean the data and deliver an initial summary report. KS analysis will continue. KS contrasts between Year 1-2 will be reported, in addition to early findings regarding Aim #3 contextual factors and implementation processes based on both waves. Additional organizational analyses with linked administrative data for Aim #2 will also be reported (e.g., variations in resource sufficiency by large and small low-performers).

In Q4, organizational changes based on KS interviews and organizational surveys between Years 1 and 2 overall and by EBQI vs. waitlisted controls will be reported to WHS. We will deliver a second annual report for WHS, summarizing findings across evaluation data sources for FY18, with notable FY17 comparisons.

**FY19**: In Q1, the EBQI contractor will launch EBQI in the remaining low-performing VA facilities. We will again update the KS sample as needed, and launch the third and final wave of KS interviews and again

extend the KS sample to accommodate EBQI targets in Groups 1 and 2 that will have had two and one year of EBQI, respectively. We will start with the baseline KS interviews for Group 3, followed by the KS followup interviews for Groups 1 and 2, which may carry over into Q2. We will again repeat OASC and Union review, and launch the third and final organizational survey wave.

In Q2, we will complete the KS interviews, and initiate rapid KS analysis. We will update the provider/staff sample for the third wave, repeat sample validation steps with participating sites, and prepare endorsement letters once again, and launch the survey by the end of Q2. By the end of Q2, we will also provide WHS with the third wave of KS summaries and an organizational survey summary in the quarterly report.

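### The Aim 2 model uses an undefined level of implementation as its primary regressor and never names the randomized roll-out status, so the effectiveness estimate may be as-treated

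*Combined protocol and SAP*

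**What the plan says.** Section B2 sets up a randomized roll-out: "EBQI implementation will commence in Year 1 (FY17) in eight randomly selected facilities (Group 1"), with 16 sites waiting, eight of those drawn at random in FY18, and the last eight starting in Year 3. It credits this design with good power and protection from outside influences.

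Section B5b is the only place where an Aim 2 effectiveness model is specified. It states: "The primary regressors of interest will be EBQI exposure (i.e., level of implementation) and time". The model is linear or logistic regression with random site intercepts. Group, launch step, waitlist status and an as-allocated rule are not mentioned.

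Other sections use the key term in two ways:

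- **Achieved uptake.** B4c lists a provider/staff measure of exposure and participation, with examples "e.g., awareness, hours spent, local buy-in".
- **Scheduled roll-out.** B6b describes the last sites "with the remainder getting EBQI exposure in Year 3", and D2 (FY19 Q1) speaks of EBQI targets "in Groups 1 and 2 that will have had two and one year of EBQI, respectively".

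Comparisons by randomized status do appear outside B5b. D2 (FY18 Q4) promises a report of organizational change in EBQI against waitlisted sites, and B4d will explore patient-survey data by group. Neither gives an estimator.

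**The concern.** Randomization protects a comparison only if the analysis uses what was randomized. Here that is the launch date. How far a site then implements EBQI is not randomized. The conceptual framework (A6) places local EBQI actions in the context of "leadership support, local resources, pre-EBQI WH care model and staffing", and each of these can plausibly affect both uptake and outcome. Sites able to implement more may have better outcomes, or improve faster, without EBQI. A coefficient on achieved level would mix that with EBQI's effect.

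Assigned and achieved exposure may well differ. B6b says: "We plan to proceed with the evaluation even if not all contracted-for activities occur". Two analysts following B5b could therefore fit models with different estimands, one randomized and one not, and both claim to have followed the plan. The properties claimed in B2 would belong to only one of them.

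**Working it through.** **1. Figures in the plan.** The documents state no effect size, SD, intraclass correlation or power for Aim 2, so there is nothing to reproduce. The textual point rests on B5b read against B2, B4c, B6b and D2. The size of the bias can only be illustrated.

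**2. Why a random intercept is not enough.** A random-intercept fit subtracts only a fraction of each site's mean:

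θ = 1 − √[σ²e / (σ²e + Tσ²u)]

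With the assumed σ²u = 0.6, σ²e = 0.4 and T = 3 waves, θ = 1 − √(0.4 / 2.2) = 1 − 0.43 = 0.57. About 43% of a stable site difference stays in the transformed data, so confounding of outcome level is reduced but not removed. Site differences in trend are not modelled at all.

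**3. Simulation set-up.** From the documents: 24 sites in groups of 8/8/8, three waves, random site intercepts. Assumed: total variance 0.6 + 0.4 = 1, so effects are in SD; true EBQI effect zero; level on a 0–1 scale with mean 0.5; correlation of level with site capacity 0.3 to 0.6. Capacity acts either on outcome level (correlation 0.3 or 0.6) or on trend (0.1, 0.2 or 0.3 SD/year). Models use categorical waves, with 5,000 trials per setting.

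Two timings follow D2, with launch dates within each year assumed:

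- *Organizational surveys* (Q1 each year): Group 1 exposed at waves 2–3, Group 2 at wave 3, Group 3 not yet.
- *Provider/staff surveys* (end of Q3 in FY17, Q2 afterwards): Group 1 exposed at waves 1–3, Group 2 at waves 2–3, Group 3 at wave 3.

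**4. Results.** Spurious effect at mean level, in SD (false positives at nominal 5%):

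| Setting | Organizational timing | Provider/staff timing |
|---|---|---|
| Capacity acts on outcome level only | 0.02–0.06 (5–6%) | 0.03–0.12 (6–10%) |
| Trend 0.1 SD/year | 0.03–0.06 (6–7%) | 0.03–0.07 (6–8%) |
| Trend 0.2 SD/year | 0.06–0.13 (7–11%) | 0.06–0.14 (7–12%) |
| Trend 0.3 SD/year | 0.10–0.19 (9–16%) | 0.10–0.20 (9–18%) |
| Level unrelated to capacity | within 0.01 (5–7%) | within 0.01 (5–7%) |
| Assigned status, every setting | within 0.01 (4–7%) | within 0.01 (4–7%) |

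The full 0-to-1 contrast is twice the mean-level figure. The sampling SD is 0.19–0.23 for the level estimate at mean level and 0.25–0.29 for assigned status.

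**5. Covariate adjustment.** B5b lists covariates such as "e.g., DWHP availability, readiness), and organizational factors (e.g., resource sufficiency, facility size". One covariate correlated 0.6 with capacity was added as a main effect:

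- *Capacity acting on outcome level (correlation 0.6).* The organizational range falls from 0.031–0.060 to 0.021–0.042, and the provider/staff range from 0.054–0.121 to 0.035–0.078. This removes about a third (for example 0.018/0.060 = 30%, 0.043/0.121 = 36%).
- *Trend 0.3.* The ranges fall from 0.096–0.186 to 0.085–0.180 and from 0.102–0.205 to 0.092–0.177. This removes 3% (0.006/0.186) to 14% (0.028/0.205).

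**6. Sensitivity to assumptions.** A second simulation used organizational timing, within-site correlation 0.5, and level fully determined by site readiness. It gave full-contrast biases of 0.18–0.20, 0.39–0.42 and 0.58–0.63 SD for the three trends, with false positives of 7–8%, 13–17% and 20–31%. Without a trend it gave none, because readiness there acted only on trend. Assigned status again averaged about zero (4.4–6.0%). The direction agrees; the size depends on how closely uptake tracks capacity.

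**The case against.** The strongest reply is that this is an ambiguity and not a demonstrated wrong analysis. Exposure plus time is the usual regressor pair for a randomized roll-out, B1 places the evaluation within the waitlisted design, and B6b and D2 use exposure in the scheduled sense. That stands, and the as-treated conclusion is conditional for this reason. The gloss in B5b and the B4c measure still lean the other way, and nothing in B5b settles it.

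Other objections:

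- **Unseen sources.** Appendices 4 and 5 may define the exposure measures, and D2 mentions a template for monitoring EBQI procedures. The safe claim is that B5b does not say which measure defines level.
- **Covariates.** B5b adjusts for readiness and resources and examines leadership support as a moderator. This reduces confounding but does not restore the randomized comparison. Because the surveys are repeated, such covariates may also be measured after launch.
- **Partial delivery.** The B6b sentence concerns contractor shortfall. It shows that assigned and achieved exposure may differ, not that site capacity is the reason.
- **Small bias.** With level-only confounding on organizational timing, false positives are close to nominal. Site fixed effects took level-only bias to at most 0.01 SD. No passage documents a capacity-driven trend.
- **Precision.** Under the null the level estimate often has the smaller root mean squared error: about 0.21 against 0.27 with organizational timing, level-only confounding and correlation 0.6.

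These limit the size of the concern. They do not make a non-randomized coefficient the right primary estimate in a randomized design.

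**Conclusion.** The concern holds. B5b should name the randomized roll-out status and does not. If achieved level is intended, the primary estimate is as-treated and biased whenever site capacity drives both uptake and outcome. If assigned exposure is intended, the text needs to say so.

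The likely bias is modest. Under the main assumptions it is below one sampling SD except in the most extreme settings, where the two are about equal. All parameters are assumed, so only the direction should be relied on. The correction is worth making before allocation, but the point is not fatal to the evaluation. Confidence is medium because the wording can be read two ways.

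**What to change.** Replace the regressor sentence in B5b with wording to this effect:

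> The primary regressor is each site's randomized roll-out status at the date of each data collection (0 before and 1 after its assigned launch date), set separately for each data source, with categorical period effects. Every allocated site is analysed in its assigned group. Level of implementation, with its source (for example the B4b or B4c survey items) and scale defined, is a secondary dose-response analysis labelled non-randomized.

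Add how a replaced site is handled, since B6b allows replacement. If level already meant assigned time on EBQI, say so and define it from the assigned launch date. In the simulations assigned time was also unbiased (within 0.01 SD/year), but its false positives reached 8–9% at a trend of 0.3 SD/year because site trends were unmodelled. Status is therefore the safer primary form, and assigned duration can be secondary.

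The cost is a few sentences and a record of assigned launch dates. No new instrument is needed, and allocation is still to come (B3, D2), so the regressor can be fixed beforehand. Poorly engaged sites must still be followed; B4b already surveys all 24 facilities at baseline, 12 and 24 months. The price is an estimate that includes imperfect implementation, may be smaller than a dose-based figure, and is less precise.

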### 02a. RESEARCH PLAN (EVALUATION PLAN)

# A. BACKGROUND

**A1. Gaps in Comprehensive Care for WVs**. Historically plagued by gaps in safety and privacy for women in VA facilities originally designed for men, with a workforce with little to no exposure to female patients, the VA has faced significant challenges in meeting WVs' complex care needs. Ensuring access to gender-specific care and a full complement of reproductive and gynecologic health services has also contributed to higher rates of community referrals among WVs, further fragmenting their care. These and other challenges have led to persistent gender disparities in VA care quality and patient experience.

Over a decade ago VA stood up a handful of comprehensive WH centers in response to Government Accounting Office findings of gaps in WVs' care, and subsequent legislation. WH clinics grew 8-fold over the next decade. However, only a fraction delivered comprehensive services like the original model programs, many focusing on gender-specific exams to help increase VA breast and cervical cancer screening rates. Nonetheless, adoption of WH clinic models was associated with higher preventive practices and higher WV ratings of access, continuity, coordination, and satisfaction.

**A2. VA Policy Aimed to Respond to Gaps in Care**. In 2010, VA WHS launched a 5-year strategic plan to redesign the nation's healthcare delivery system for WVs, with guidance on required use of designated WH providers (DWHPs) for primary care (PC), acceptable PC model features with integrated MH and gender-specific care, and a set of required comprehensive services (VHA Handbook 1330.01, May 2010). Added were explicit expectations that all VA care environments must afford WVs a sense of safety/security, supply same-gender providers (if preferred), and address gender-sensitivity across the spectrum of VA services.

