Our evaluation activities map directly to this conceptual framework using a formative evaluation framework designed to identify the potential and actual influences on progress and effectiveness of implementation efforts. For example, we will evaluate the EBQI contractor's implementation of EBQI methods (*first column*) under **Aim #1** as a developmental evaluation stage (e.g., degree of less-than-best practice, determinants of current practice, barriers/facilitators and feasibility/perceived utility). Under **Aim #2**, we will conduct a progress-focused evaluation of EBQI effectiveness on achievement of comprehensive care (right column), monitoring impacts and indicators of progress toward goals, with feedback to WHS and the EBQI contractor. **Aim #3** will cover two types of evaluation. First, we will conduct an implementation-focused evaluation (also known as process evaluation) to examine discrepancies between EBQI implementation plans and how the EBQI contractor actually operationalizes them, helps identify influences we might otherwise have not considered, will enable us to describe experiences of those undergoing EBQI implementation, and will consider the context in which facilities participate (12-month key stakeholder interviews [**§B4a**] will be especially important). Second, we will use results from all of the other evaluation stages to conduct an interpretive evaluation (24-month key stakeholder interviews will be key here).

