B4a. Key Stakeholders (KS). Semi-structured gualitative interviews will be conducted at baseline for all sites (Aim #1), as well as immediately prior to the EBQI launch of Groups 2 and 3. Interviews will be conducted at all sites at 12 months post-EBQI launch; in Group 1, interviews will also be conducted at 24 months. Sampling Plan: For Aim #1, we will work with the EBQI contractor to identify facility-level KS (e.g., quadrad member, PC director, WH medical director, WVPM, QI/system redesign lead; n~6/facility) and VISN-level KS (e.g., VISN director, VISN Lead WVPM, VISN system redesign lead; n~4/VISN). We will also interview WHS leaders and EBQI contractor personnel to evaluate leadership and implementation processes. We will adapt KS selection based on the QI targets established at initial EBQI site visits (e.g., add a MH director if the QI project targets MH). For Aim #3, we will seek to re-interview the same KS as in Aim #1, but will pursue replacement personnel in the event of turnover and/or position changes over time. Measures: The Aim #1 baseline interview guide (Appendix 3) includes guestions about the structure and delivery of usual care for WVs, barriers and facilitators to achieving delivery of comprehensive WH care, what (if any) improvements are underway in WH and/or for WVs, familiarity with performance metrics, access to metrics by gender, experience with QI, local culture, perceptions of the care environment, and engagement. The Aim #3 12- and 24-month interviews will assess any changes in care for WVs (staffing, structure, etc.), details of completed/in progress QI projects, perspectives on critical components of EBQI, and anticipated sustainability of local improvements and QI methods. Data Collection: Under the supervision of [name] (Co-PI), KS interviews will be conducted by telephone, recorded and professionally transcribed. Transcripts will be reviewed and edited for accuracy.

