#### D. MANAGEMENT PLAN AND TIMELINE

**D1. Management Plan**. The core team ([name], [name], [name], [name], [name], [name], [name]) will meet weekly, with biweekly Aim-specific meetings focused on evaluation sub-aims (e.g., KS interviews). Monthly

WHS calls already underway will continue throughout the PEC's evaluation period, with additional emails and calls arranged to meet Partner information needs and obtain WHS review/input. We will also participate in regular WHS calls with the EBQI contractor (see *Organizational Chart* in **Appendix 7**). Drs. [name] and [name] will attend 1-2 of the initial in-person EBQI meetings and join initial site engagement calls.

**D2. Timeline/Deliverables**. We will deliver written quarterly reports and briefings to WHS throughout the evaluation, consistent with current practices in annual WHS Memoranda of Understanding (MOUs). The FY17 MOU has already been finalized and will be signed before QUERI PEC review but for a reduced scope of work. Deliverables (below) will be appended to the MOU in Quarter 1 (Q1) if the PEC is awarded.

**FY17:** In Q1, we will work with WHS and the EBQI contractor to finalize operational criteria for classifying low-performing VA facilities. We will review the draft KS interview guide (**Appendix 3**) and provider/staff surveys (**Appendix 5**) with WHS, incorporating WHS and other subject matter experts' feedback as requested. WHS has already approved the organizational survey modules for FY17 (**Appendix 4**); these will be fielded in Q1. WHS will launch facility leadership introductions (including notification of evaluation plans), affirming participation, after which we will randomly allocate sites to EBQI (n=8) or waitlisted control (n=16). We will support contractor training in EBQI technical specifications in collaboration with WHS, document training, and develop a template for use in monitoring EBQI procedures used.

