In Q2, WHS and the EBQI contractor will identify local champions and evaluation contacts for our use in identifying KS and launching baseline interviews across all sites. Organizational survey data will be cleaned and a report of initial frequencies provided to WHS. Provider/staff surveys will be submitted to OASC when released by WHS, after which we will submit them for national Union review; endorsement letters will be drafted for WHS review, and adapted to fit local contexts and needs, while we simultaneously obtain and begin validating sample lists. We will also pull and analyze the administrative data for participating sites.

In Q3, we will deliver KS summaries to WHS, while beginning to conduct the more in-depth ATLAS.ti analyses. We will finalize the provider/staff surveys following OASC and Union review, program them in REDCap, and launch survey administration by the end of Q3. We will conduct an organizational analysis of the 24 participating low-performers compared to higher performers of similar complexity.

In Q4, we will provide results for Aim #1 (barriers/facilitators) to WHS in the form of presentations and summary reports for each group of sites. We will finish provider/staff survey follow-up, with concurrent data cleaning and quality checks, followed by analysis and reporting to WHS of baseline evaluation findings for Aim #2. We will generate an annual report for WHS, summarizing evaluation findings across all data sources for FY17.

**FY18**: In Q1, we will randomly allocate the next 8 VA facilities to EBQI, update the KS sample, and launch the second wave of KS interviews, focusing first on baseline for newly allocated EBQI VAs. We will restart the OASC and national Union review procedures, adapting to FY18 blackout dates, and launch the second wave of the organizational surveys.

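### Does B5b's silence on when covariates and moderators are measured put the EBQI effect estimate at risk?

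*Combined protocol and SAP*

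**What the plan says.** B5b (Quantitative Analyses, Aim #2) makes EBQI exposure and time the main regressors, in hierarchical models with random site intercepts. Adjustment is to be made where appropriate. The example covariates are patient factors (casemix, share of women Veterans seen), "provider/staff factors (e.g., DWHP availability, readiness), and organizational factors (e.g., resource sufficiency, facility size". On moderation it says "We will examine the potential moderating effects of practice context and provider/staff knowledge/attitudes", with high versus low leadership support as the example. No wave is given for any of these variables.

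Readiness and staff attitudes come from the provider/staff survey (B4c). Leadership support and resource sufficiency come from the organizational survey (B4b). Both surveys are repeated at baseline, 12 and 24 months.

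Two other places bear on timing:

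- **A6 (Conceptual Framework).** Care model, staffing, and staff experience and attitudes carry a pre-EBQI tag. Leadership support and local resources sit in the same list of context in which EBQI acts, without the tag. Readiness is not named. A6 adds: "Our evaluation activities map directly to this conceptual framework".
- **D2 (Timeline).** In FY17 Q1 facilities affirm participation, "after which we will randomly allocate sites to EBQI (n=8) or waitlisted control (n=16"). The organizational survey is fielded in the same quarter. For the first provider/staff survey, the team will "launch survey administration by the end of Q3" of FY17. In FY19 Q1 "the EBQI contractor will launch EBQI in the remaining low-performing VA facilities". Group 1's launch quarter is not stated.

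**The concern.** A longitudinal model with repeated covariates can easily be fitted with each covariate taken from the same wave as the outcome. If EBQI has already moved that covariate, the model estimates only the part of the effect that bypasses it, and EBQI looks weaker than it is. With 24 facilities, which B5b itself calls a small number for site-level effects, that loss could hide a real benefit. Splitting sites on a post-launch moderator dilutes the effect within each subgroup in the same way.

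Some of the listed variables could well respond to EBQI. Staff attitudes are an Aim #2b outcome. For staffing, B4a says the "12- and 24-month interviews will assess any changes in care for WVs (staffing, structure, etc".), and A2 describes national policy as including "guidance on required use of designated WH providers (DWHPs) for primary care (PC"). Writing the word baseline into B5b might not settle the matter either. The first provider/staff survey follows allocation by up to two quarters, so it may come after launch in Group 1.

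**Working it through.** The plan states no effect size, power or alpha for this question, so there is no figure to reproduce. The check has four parts.

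**1. What the documents say about each variable**

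| Variable | Role in B5b | Timing cue in A6 | Do the documents say EBQI changes it? |
|---|---|---|---|
| Facility size, casemix | covariate | none needed | no, and unlikely |
| DWHP (designated women's health provider) availability | covariate | staffing is tagged pre-EBQI | indirectly: B4a asks an open question about change; the A2 policy also binds waitlisted sites |
| Resource sufficiency | covariate | context, untagged | not stated |
| Readiness | covariate | not named | not stated |
| Leadership support | moderator | context, untagged | A5 reports early evidence that EBQI activates leadership |
| Staff knowledge/attitudes | moderator | attitudes and awareness tagged pre-EBQI | yes (Aim #2b, A6) |

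The one variable that is plainly an EBQI target is also one that A6 tags as pre-EBQI when it serves as context.

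**2. How many same-wave values would fall after launch**

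There are 24 sites × 3 waves = 72 facility-waves.

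- Organizational survey, counting a survey in the launch quarter as pre-launch: 8 × (2 + 1 + 0) = 24 of 72.
- Provider/staff survey: 8 × (2 + 1 + 1) = 32 to 8 × (3 + 2 + 1) = 48 of 72, depending on when Groups 1 and 2 launch.

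So the opportunity for the error exists.

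**3. Size of the bias if same-wave values were used (all inputs assumed)**

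Let a be the EBQI effect on the covariate and b the covariate's effect on the outcome. The adjusted estimate is then about the total effect minus a × b. With an assumed total of 0.50 (2,000 simulated trials per setting):

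- a = 0: expected 0.50, simulated 0.49 to 0.51
- a = 0.3, b = 0.2: 0.50 - 0.06 = 0.44, simulated 0.44
- a = 0.6, b = 0.4: 0.50 - 0.24 = 0.26, simulated 0.25
- a = 0.6, b = 0.6: 0.50 - 0.36 = 0.14, simulated 0.14

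The loss is the mediated share that was put in, so the simulation says nothing about how large that share is here.

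The first-wave question was checked with an assumed total of 0.60, of which 25%, 50% or 75% runs through the covariate. If Group 1 launched before the first provider/staff survey, adjusting for that wave gives 0.57, 0.55 and 0.50, shortfalls of 0.03, 0.05 and 0.10. If Group 1 launched after it, the estimate is within 0.003 of the unadjusted one.

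**4. Would a fixed rule for moderators improve matters?**

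The natural rule is to split sites on leadership support in the FY17 Q1 organizational survey. That survey is also the first outcome wave for service availability and the other organizational measures.

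The inputs, all assumed, were: EBQI shifts the moderator by 0.6; outcome slope on the moderator 0.5; site and residual variances 0.5 each; shared site factor SD 0 or 0.5; wave 1 before every launch; true effect 0.60 in both halves.

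| Split | Low | High | High minus low |
|---|---|---|---|
| FY17 Q1 value | about 0.73 | 0.46 to 0.50 | -0.23 to -0.27 |
| FY17 Q1 value with moderator-by-wave term | – | – | close to zero |

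The cause is regression to the mean. Sites that score high by chance in wave 1 also have high wave-1 outcomes, all unexposed, which then fall back. A same-wave split gives almost no false contrast. It does dilute the effect, to 0.41–0.46 in each half in runs on the provider/staff launch patterns.

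**The case for a change.** The strongest case for a change is that the gap is real and cheap to close. B5b gives no wave, and A6 is a conceptual framework whose tags are not carried into the model and do not cover leadership support, resources or readiness. The qualifier about adjusting where appropriate governs whether to adjust, not when the covariate is measured. D2 also says that in FY19 Groups 1 and 2 will have had two years and one year of EBQI. That suggests Group 1 launched early in FY17, ahead of the provider/staff survey, so that its first answers could be post-launch.

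Most of this stands as description. A sentence naming pre-launch values would do no harm, and anyone using first-wave readiness or attitudes should look at Group 1's actual launch date. What does not stand is the step from an unstated detail to a faulty plan. Taking covariates and moderators from before the intervention is ordinary practice, the framework points the same way, and nothing in the plan contradicts it. The launch date is inferred from rounded durations, and an EBQI effect on readiness or resources is plausible but nowhere stated.

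**Conclusion.** No change to the plan is called for. B5b omits a measurement time, and a competent analyst would fill that gap sensibly with pre-launch values; no stated rule would put post-launch values into the effectiveness model.

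The possible loss equals whatever part of the EBQI effect runs through a same-wave covariate, and is nil if EBQI does not move it. The documents do not allow that part to be sized. The narrower worry about the first provider/staff wave amounts to 0.03 to 0.10 on an assumed effect of 0.60, and only if Group 1 had already launched.

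A simple rule fixing moderators at FY17 Q1 could do harm of its own for outcomes from the same survey, unless the model also lets the moderator's association with the outcome differ by wave.

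This conclusion rests on reading A6 as a guide to intent and on the analysts following usual practice. It would change if an analysis specification actually called for same-wave readiness, resources, leadership support or attitudes in the effectiveness model.
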